### **Specific Aims:**

**Primary Aim 1:** Assess the effect of using a videolaryngoscope versus direct laryngoscope for the initial laryngoscopy on the number of intubation attempts in patients having cardiac, thoracic, or vascular surgery.

**Primary Hypothesis 1:** Fewer intubation attempts are required when initial laryngoscopy is performed with a videolaryngoscope rather than a direct laryngoscope in patients

having cardiac, thoracic, or vascular surgery. Any reduction in intubation attempts will be considered clinically meaningful.

**Primary Outcome:** The number of intubation attempts with the initial laryngoscopy instrument.

**Secondary Aim 1:** Compare intubation failure rates with videolaryngoscopy and conventional direct laryngoscopy, with failure defined by the clinician switching to an alternative laryngoscopy method.

**Secondary Hypothesis 1:** There are fewer intubation failures when laryngoscopy is initially attempted with a videolaryngoscope rather than a direct laryngoscope. Any reduction in intubation failures will be considered clinically meaningful.

**Secondary Outcome 1:** Intubation failure, defined by the clinician switching to an alternative laryngoscopy method.

**Secondary Aim 2:** Compare airway and dental injuries when laryngoscopy is initially attempted with a videolaryngoscope rather than a direct laryngoscope.

**Secondary Hypothesis 2:** A composite of airway and dental injuries is less common when laryngoscopy is initially attempted with a videolaryngoscope than with a direct laryngoscope. A reduction with a number-needed-to-treat <100 will be considered clinically meaningful.

**Secondary Outcomes 2:** Any dental and/or airway injury, defined as any bleeding or apparent injury.

**Exploratory Hypothesis 1:** Intubation assisted by videolaryngoscope provokes less hypertension and tachycardia than direct laryngoscopy. Differences in mean arterial pressure >10 mmHg and/or in heart rate of at 10 beats/minute will be considered clinically meaningful.

**Exploratory Outcomes 1:** Maximum mean arterial pressure and heart rate in the 5 minutes after intubation.

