**Measurements:** All data will be obtained from electronic anesthesia and hospital records. No tests or evaluations will be done specifically for this trial. Preoperative airway characteristics and difficulties encountered during anesthetic induction will be recorded per routine (*table 1*). Demographic and morphometric characteristics will be obtained from the electronic records including age, sex, race, and body mass index. Type of surgery will be characterized from ICD-10 codes using AHRQ Clinical Classifications Software. All routine anesthetic variables, including medications, will be recorded by routine by our electronic anesthesia record keeping system. We will also capture the level of training of the person making the first intubation attempt and the final intubation attempts (if a switch of anesthesia providers occurred).

Table 1:

Preoperative airway characteristics	Neck- full range of motion
	Limited neck extension
	Limited neck flexion
	Limited neck extension and flexion
	Short neck
	Short thyromental distance
	Small mouth opening
	Non-compliant submandibular space
	Beard presents
Difficulties encountered during anesthesia induction	Anterior larynx
	Expected difficulties
	Large epiglottis
	Large tongue
	MAC safe cannula
	Poor jaw range of motion
	Poor neck range of motion

	Recessed chin
	Sniffing position
	Stylette required
	Unexpected difficulties

Per our clinical routine, an initial attempt will be defined by insertion of a laryngoscope blade and/or endotracheal tube into a patient's mouth. Subsequent attempts will be defined by re-insertion of an endotracheal tube, or insertion of the same or a new laryngoscope blade. Attempts will be recorded per routine by anesthesia providers in the electronic record.

*Intubation failure* will be defined by the responsible clinician switching to an alternative laryngoscopy device for any reason at any time, or by more than 3 intubation attempts.

*Airway injury* will be defined as any bleeding or apparent injury to the lips, mouth, pharynx, vocal cords, or other airway structures recorded by the anesthesia team.

*Dental injury* will be defined as any apparent injury to the teeth as recorded by the anesthesia team.

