### **Statistical Analysis:**

We will assess the balance of randomized groups (videolaryngoscopy vs. direct laryngoscopy) on baseline and demographic characteristics using the absolute standardized difference (ASD), defined as the absolute difference in means, mean ranks, or proportions divided by the pooled standard deviation. Any characteristics with  $ASD > \text{maximum of } 0.10 \text{ and } 1.96\sqrt{(n_1 + n_2)x(n_1n_2)}$  will be considered imbalanced and will be adjusted for in the primary and secondary analyses.

All primary and secondary analyses will use the modified intent-to-treat principle, including all randomized patients who received any of the study. We will conservatively assign all missing outcome values as the highest possible score in the control group (direct laryngoscopy) and the lowest possible score in the treatment group (GlideScope videolaryngoscopy) for all primary and secondary analyses. Assumptions of statistical tests will be assessed using graphical and statistical methods.

For the primary outcome, number of intubation attempts will be calculated as the number of attempts with either device, independent of whether or not a patient was crossed over to the other device due to failure with the randomized device. The ordinal categories will be 1, 2, 3, and  $> 3$  attempts. We will assess the effect of videolaryngoscopy vs. direct laryngoscopy on the number of intubation attempts using a generalized linear mixed effects cumulative logit model in which we consider the outcome to be ordinal and consider the operating room within cluster as a random effect. In sensitivity analyses we will assess the treatment effect using a Wilcoxon-Mann-Whitney test and a proportional odds logistic regression model, if the assumption of proportional odds holds. In all analyses, we will adjust for variables imbalanced at baseline.

For the secondary (binary) outcomes of 1) intubation failure and 2) collapsed composite of any airway or dental injury we will assess the effect of videolaryngoscopy vs. direct laryngoscopy using a generalized linear mixed effects model in which we consider the outcome to be binary and consider the operating room within cluster as a random effect.

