**Interim Analyses.** We will conduct interim analyses for efficacy and futility at each 25% of the planned enrollment using a group sequential design with a gamma spending function, with gamma parameter of -4 for efficacy and -1 for futility. Assuming the alternative hypothesis is as specified below in Sample Size Considerations, there will be a cumulative 9.4% probability of crossing a stopping boundary at the first look, 40% through the 2nd look, 78 % through the 3rd look and 100% by the last. Stopping boundaries will *not* be binding – the decision to stop or continue the trial will be made by the DSMB which will consider all available information in their decision.

**Sample size considerations.** Sample size is based on the primary outcome, the number of intubation attempts (with either device). About 5,000 operations per year will be performed during the anticipated 3-year enrollment period. Based on a previous study, we expect that about 10% of patients may require more than 1 intubation attempt in the direct laryngoscopy group versus about 4% in the videolaryngoscopy group. (Direct laryngoscopy 1 attempt: 90%, 2 attempts: 4%; Videolaryngoscopy 1 attempt: 96%, 2 attempts: 4%). However, we plan the study to detect a slightly smaller effect, which also would be clinically relevant.

We assume for sample size calculation that the proportion having 1, 2, 3 or more than 3 attempts will be 0.90, 0.04, 0.03, 0.03 in the direct laryngoscopy group and 0.92, 0.04, 0.02, 0.02 with videolaryngoscopy. To detect this difference or a larger one with 90% power at the 0.05 significance level with a Mann-Whitney test we would need a total of 8,800 patients, before accounting for interim analyses or within-cluster correlations. Accounting for a small within-cluster correlation of 0.01 and even smaller within-cluster

between-period correlation of 0.009, the required total sample size  is 13,112. Further adjustment for interim analyses requires a maximum total of 14,943 patients.

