**Trial timeline:**

08/20/2019	study protocol version 1 finalized
09/11/2019	initial submission of study protocol version1 submitted to IRB
12/24/2020	IRB approval granted (study protocol version 4)
01/08/2021	trial registration on www.clinicaltrials.gov
03/15/2021	Start of clinical training
03/29/2021	First patient enrolled
06/11/2021	AE reported to IRB
02/26/2022	enrollment paused due to transfer of documentation from ARKS to EPIC
03/14/2022	enrollment restarted

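### The missing-outcome rule is called conservative, but it scores missing direct-laryngoscopy patients worst and missing videolaryngoscopy patients best, so it favours the tested device

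*Combined protocol and SAP*

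**What the plan says.** The second paragraph of Statistical Analysis sets one rule for missing outcomes: "We will conservatively assign all missing outcome values as the highest possible score in the control group (direct laryngoscopy) and the lowest possible score". It continues with "the lowest possible score in the treatment group (GlideScope videolaryngoscopy) for all primary and secondary analyses". Both arms and both devices are named, so the direction is not in doubt.

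Primary Hypothesis 1 in Specific Aims is "Fewer intubation attempts are required when initial laryngoscopy is performed with a videolaryngoscope rather than a direct laryngoscope". The two secondary hypotheses likewise predict fewer failures and fewer injuries with videolaryngoscopy. The primary outcome is scored 1, 2, 3 or more than 3 attempts; the secondary outcomes are binary.

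On data sources, the Measurements section says: "Attempts will be recorded per routine by anesthesia providers in the electronic record". Dental injury is defined as "any apparent injury to the teeth as recorded by the anesthesia team", and airway injury is defined in the same way. No expected rate of missing outcomes is given. The sensitivity analyses for the primary outcome change the test or model, not the missing-data rule. The Interim Analyses paragraph makes no exception to it.

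**The concern.** Under this rule a direct-laryngoscopy patient with no recorded outcome is counted as needing more than 3 attempts, or as a failure or an injury. A videolaryngoscopy patient with no recorded outcome is counted as a first-attempt success, or as free of failure or injury. For a trial meant to show that videolaryngoscopy is better, a conservative assignment would run the other way. The arms may have been transposed in drafting, but an analyst who follows the text would build in a bias toward the tested device.

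The rule governs the primary analysis, the secondary analyses and, by default, the efficacy looks. At stake is the false-positive rate for the main claim. The planned effect is only 2 percentage points, so a small missing fraction is enough to matter.

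**Working it through.** **Inputs.** From Sample size considerations: direct laryngoscopy (DL) 0.90/0.04/0.03/0.03 and videolaryngoscopy (VL) 0.92/0.04/0.02/0.02 for 1, 2, 3 and >3 attempts; significance level 0.05; total N of 8,800, then 13,112 with clustering, then 14,943 with interim looks. Allocation is 1:1. Three things are my assumptions: the missing rate m (0.1% to 2%, equal in both arms and random), a two-sided reading of the 0.05 level (2.5% in favour of VL), and the true failure rate.

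**The plan's own figure.** A continuity-corrected two-proportion calculation for 10% v 8% at 90% power gives about 8,800, which matches "we would need a total of 8,800 patients, before accounting for interim analyses or within-cluster correlations". The Mann-Whitney test that the plan names would need about 7,975 on the four categories, so its power at 8,800 is 92.6%. This does not affect the point here.

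**Effective sample size.** The clustering inflation is 13,112 / 8,800 = 1.49, so the maximum N is worth 14,943 / 1.49 = 10,029 independent patients. Treating all 14,943 as independent gives an upper bracket.

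**Size of the false difference.** Take the DL distribution in both arms, so that there is no true difference:

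- DL, more than one attempt: (1 − m) × 0.10 + m
- VL, more than one attempt: (1 − m) × 0.10
- Gap: m

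**Worked case, m = 1%, N = 10,029.**

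- DL becomes 0.8910/0.0396/0.0297/0.0397 and VL becomes 0.9010/0.0396/0.0297/0.0297.
- θ = P(DL > VL) + ½P(tie) = 0.10214 + 0.40321 = 0.50535.
- With pooled category shares p, the tie-corrected SE = √[(1 − Σp³) / (3N)] = √[0.28055 / 30,087] = 0.00305.
- z = 0.00535 / 0.00305 = 1.75, so P(significant for VL) = P(Z > 1.96 − 1.75) ≈ 0.417.

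**Range.** Simulated chance of a false VL benefit on attempts (200,000 trials per scenario, tie-corrected Mann-Whitney). The four-look column uses the gamma(−4) efficacy boundary at equal looks, with z bounds 3.155, 2.818, 2.439 and 2.014.

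| Missing per arm | >1 attempt, DL v VL | 10,029, single test | 10,029, four looks | 14,943, single test |
|---|---|---|---|---|
| 0.1% | 10.09% v 9.99% | 3.7% | 3.7% | 4.1% |
| 0.25% | 10.23% v 9.98% | 6.3% | 6.3% | 7.7% |
| 0.5% | 10.45% v 9.95% | 14% | 14% | 19% |
| 1% | 10.9% v 9.9% | 42% | 41% | 57% |
| 2% | 11.8% v 9.8% | 93% | 93% | 99% |

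With no missing data the figure is 2.5%.

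**If VL were truly worse by the planned amount** (10% VL v 8% DL), 2% missing would hide it: DL 0.98 × 8% + 2% = 9.84%; VL 0.98 × 10% = 9.80%.

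**Intubation failure** (two-proportion z test, N = 10,029, equal true rates). At 0.1/0.25/0.5/1/2% missing, a 3% true rate gives 4.8/11/29/78/>99%, and a 5% rate gives 4.2/8.3/20/60/99%.

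**Alternatives at 1% missing, N = 10,029.** Analysing observed outcomes keeps the false-benefit rate at 2.5% and power at 95%. Swapping the arms in the rule gives 40% power and a 42% chance of falsely finding VL worse.

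**The case against.** The strongest reply is that the harm depends on a missing rate the documents do not give. Attempts and failure are known within minutes of intubation, need no follow-up visit and are charted routinely, so few values may be missing. At 0.1% missing the error is 3.7% rather than 2.5%. This stands as a limit on size, not on direction. At 0.5% missing the error is already more than five times nominal.

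The distortion is also uneven. Most patients succeed at the first attempt, so scoring a missing VL patient as 1 is usually right. At 10,029 patients and 1% missing in one arm only, the false-benefit chance is 35% if the gaps are all in DL and 3.6% if they are all in VL. That is correct: nearly all of the bias comes from missing DL records.

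The Trial timeline entry "enrollment paused due to transfer of documentation from ARKS to EPIC" is weak evidence of missing data, because enrolment stopped during the transfer. It shows only that the record system differed before and after.

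For failure, the 3% rate is the plan's DL share with >3 attempts. Failure also includes any change of device, so the true rate could be higher and the effect smaller: 44% at an 8% rate and 37% at 10%, with 1% missing. For injury, the bias may be small or absent if no entry is read as no injury.

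Swapping the arms is the smallest edit and is workable if very little is missing: power at 10,029 is 93%, 88% and 76% at 0.1%, 0.25% and 0.5%. It still replaces one bias with another.

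Finally, the Methods section promises a full analysis plan before data are evaluated. That is an opportunity to correct the rule; it does not correct the text as it stands.

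**Conclusion.** The rule is wrong as written and must be fixed. It is the best case for videolaryngoscopy under a conservative label, and it cannot favour direct laryngoscopy. The bias vanishes only with complete data, or if every missing DL patient truly had the worst score and every missing VL patient truly had the best.

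The direction follows from the text alone. The size is conditional on the assumed missing rate, equal and random missingness, the two-sided reading of 0.05, and the Mann-Whitney test used for the sample size in place of the planned mixed cumulative logit model. The effective N uses the plan's own clustering inflation; a smaller inflation would make the bias larger, as the 14,943 column shows.

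**What to change.** Delete the rule from the primary and secondary analyses, interim looks included, and put in its place:

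1. **Primary approach.** Analyse observed outcomes in the planned mixed models. Multiple imputation under missing-at-random, from recorded covariates, is an acceptable alternative. Name one of the two as primary before any data are evaluated.
2. **Reporting.** Give the number of missing values by arm for each outcome, and state whether the absence of an injury entry means no injury.
3. **Sensitivity analysis.** Use the reversed assignment (missing VL = highest score, missing DL = lowest) only as a worst-case or tipping-point analysis.

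Observed-outcome analysis costs one sentence of wording. Multiple imputation needs modest extra work: an imputation model for a clustered ordinal outcome, pooling, and a rule for each interim look. Neither needs new patients or new data.

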**Methods:** This research project will be conducted with Cleveland Clinic IRB approval and waived patients consent. (see Human Subjects section for justification). The trial will be registered at ClinicalTrials.gov (NCT04701762, date of registration January 8 2021) before enrolling any patients. A full statistical analysis plan will be developed before any data are evaluated. Reporting will be consistent with the CONSORT guidelines for pilot trials.

**Design:** The proposed quality improvement project will be conducted in an isolated set of 22 operating rooms (J operating suites) at the Cleveland Clinic Main Campus which is largely staffed by a consistent team of anesthesia attendings, nurse anesthetists and anesthesia residents and fellows with variable level of experience. Most operations in this suite are cardiac, thoracic, or vascular surgeries. Nearly all require general anesthesia, and most patients are hospitalized at least overnight.

We plan a cluster randomized multiple crossover quality improvement project. The J operating suites will be divided into 2 separate clusters consisting of 11 operating suites each (cluster 1: operating suites 60 to 70, and cluster 2: operating suites 71 to 81). Clusters were formed by physical proximity to make it as logistically feasible as possible to conduct the trial.

Randomization will consist of randomizing cluster 1 to use either videolaryngoscope or direct laryngoscope, and cluster 2 to the alternative device in one-week blocks.

Randomization, 1:1 and unstratified, will be based on computer-generated codes maintained in a web-based system that investigators will access one day before each new treatment block begins. Randomization allocations will be verbally communicated to anesthesia personnel directly and by signs prominently displayed on each anesthesia machine. In previous similar trials, compliance with designated allocations exceeded 97%.

Design notes: Cluster randomized multiple crossover cluster trials are analogous to individual patient crossover trials, except that each cluster is crossed over to the other treatment in the next period instead of individual patients crossing over. They differ from cluster randomized trials (CRT) in that each cluster receives each treatment multiple times instead of each cluster only receiving one of the interventions during the trial.

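### The plan names no estimate or interval that accounts for its four interim looks, so after an efficacy stop at the first or second look the ordinary model would overstate the benefit

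*Combined protocol and SAP*

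**What the plan says.** The Statistical Analysis section gives one primary analysis: "We will assess the effect of videolaryngoscopy vs. direct laryngoscopy on the number of intubation attempts using a generalized linear mixed effects cumulative logit model", with operating room within cluster as a random effect. The sensitivity analyses are a Wilcoxon-Mann-Whitney test and a proportional odds model.

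The Interim Analyses paragraph says "We will conduct interim analyses for efficacy and futility at each 25% of the planned enrollment". Both boundaries come from gamma spending, with parameter -4 on the efficacy side and -1 on the futility side. The paragraph states cumulative crossing probabilities under the planned effect of 9.4%, 40%, 78% and 100%. It also says that the boundaries are not binding and that the DSMB decides.

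Neither paragraph gives a confidence level, a sequentially adjusted interval or p-value, or a bias-adjusted estimate. The Methods paragraph says that a full SAP will be developed before data are evaluated. The combined document supplied contains no further text on this point.

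**The concern.** A spending function fixes the error rate of the test. It does nothing to the estimate or interval read from the model at the stopping look. A trial that stops early for efficacy stops because its estimate was large, so the unadjusted estimate is too large on average, most of all at the earliest looks.

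This matters here for two reasons. By the plan's own figures, 78% of trials at the planned effect cross a boundary before the last look, so an early stop is the expected outcome. And the Background says the device's extra cost is justified only if it improves success and reduces trauma. For the primary outcome the Specific Aims set no minimum worthwhile effect, so readers will weigh that cost against the reported odds ratio and its interval.

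**Working it through.** **Inputs (Sample size considerations and Interim Analyses).** The effect is "0.90, 0.04, 0.03, 0.03 in the direct laryngoscopy group and 0.92, 0.04, 0.02, 0.02 with videolaryngoscopy". For more than one attempt the odds ratio is (0.08/0.92)/(0.10/0.90) = 0.783, a log odds ratio of -0.245. Power is 90% and alpha 0.05, with sidedness not stated and two-sided assumed. Looks are at t = 0.25, 0.50, 0.75 and 1. N is 13,112 before and 14,943 after the interim adjustment.

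**Reproducing the plan's figures.**
- Efficacy spending per side: 0.025(1 − e^(4t))/(1 − e^4). At t = 0.25 this is 0.0008, so |z| = 3.155. The later boundaries are 2.818, 2.439 and 2.013.
- Futility spending: 0.10(1 − e^t)/(1 − e). At t = 0.25 this is 0.0165. The futility boundaries are |z| below 0.092, 0.490 and 1.278.
- The drift that gives 90% power is 3.458. A fixed design needs 1.960 + 1.2816 = 3.2415. Inflation is (3.458/3.2415)² = 1.138, and 13,112 × 1.138 gives about 14,925, against the stated 14,943 (ratio 1.1396).
- Cumulative crossing is 9.3%, 40.0% and 77.9%, against the stated 9.4%, 40% and 78%.

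The design therefore reproduces.

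**Look 1 by hand.** Under the planned effect, Z at look 1 is normal with mean 3.458 × √0.25 = 1.729 and variance 1.
- P(Z > 3.155) = P(N > 1.426) = 0.077.
- E(Z | Z > 3.155) = 1.729 + φ(1.426)/0.077 = 1.729 + 1.876 = 3.605. Ratio to truth: 3.605/1.729 = 2.09.
- The smallest ratio that can cross is 3.155/1.729 = 1.82, so every look-1 efficacy stop for videolaryngoscopy overstates an effect of the planned size.
- The ordinary interval covers when Z is at most 1.729 + 1.96 = 3.689. Coverage given the stop is (0.077 − 0.025)/0.077, about 67%.

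**All looks, by simulation (2,000,000 trials, both boundaries followed).**

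| Efficacy at | Share of trials | Mean log-odds estimate / truth | Odds ratio corresponding to that mean (planned 0.78) |
|---|---|---|---|
| Look 1 | 7.7% | 2.09 | 0.60 |
| Look 2 | 28.5% | 1.39 | 0.71 |
| Look 3 | 35.1% | 1.03 | 0.78 |
| Final | 18.6% | 0.79 | 0.82 |

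Early efficacy stops together are 71% of trials, with a mean ratio of 1.29. Over all trials the mean ratio is 1.09 and the median about 1.06.

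**Coverage of the ordinary 95% interval at the planned effect.** It is 92.4% with both boundaries followed and 94.1% if futility crossings are never acted on. Of the 7.6 points of non-coverage, futility stops (6.5% of trials, 46% coverage) supply 3.5, and look-1 efficacy stops supply about 0.077 × 0.33 = 2.5. A one-sided 0.025 design gives 91.2% in place of 92.4%.

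**Larger true effects, both boundaries followed.** Coverage is 95.5% at 1.5 times the planned effect and 96.0% at 2 times. At 3 times the mean estimate is about 0.5% high with 96% coverage. The 10% versus 4% that the investigators expect is ln[(0.90/0.10)/(0.96/0.04)]/ln(0.783) = 4.0 times the planned log odds. There the ratio is 1.00 and coverage 95.0%.

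**The adjusted interval.** A stagewise-ordering interval on the efficacy boundary has a median-unbiased point estimate and covers 95.0% when futility stops are not acted on, and about 93.3% when all of them are.

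**The case against.** Four arguments deserve weight.

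1. *The coverage loss is largely a futility effect.* This stands. Among winning trials the ordinary interval covers 96.1%, and futility stops understate the effect. A reader might infer from 92% that efficacy stopping alone spoils the interval. The documents do not support that, because the futility boundary is non-binding and without it coverage is about 94%.
2. *Overstatement given a win is not all due to looks.* This also stands. At half the planned effect a win overstates about 1.8-fold, and it is tempting to blame the interim analyses. A fixed design with 90% power at the planned effect and no looks gives about 1.63-fold under the same conditioning. With both boundaries followed, the mean over all trials at that effect is about 0.945 of the truth.
3. *The expected effect is larger than the planned one.* If 10% versus 4% is right, the problem vanishes. But the trial was deliberately sized for 10% versus 8%, and its stated stopping probabilities refer to that effect.
4. *Use of the ordinary interval is inferred from silence, and a full SAP is promised.* That is fair. It cannot be said that the sponsor has chosen an unadjusted interval. But the only estimation method named is the ordinary model, and followed as written it gives the figures above.

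None of these removes the inflation at look-1 and look-2 efficacy stops, which is the same whether or not futility is acted on.

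**Conclusion.** The point holds as a gap in estimation, not in testing. At the planned effect about 36% of trials (7.7% + 28.5%) would stop for efficacy at look 1 or 2, with ordinary estimates averaging 2.1 and 1.39 times the truth. Look-3 stops, the commonest, are only about 3% high. Overall coverage falls short by about one point, or by between two and three if futility is also followed. The serious local failure is 67% coverage after a look-1 efficacy stop.

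These figures assume a two-sided 0.05 design, looks at exact quarters of information, a model estimate with independent normal increments, and stopping whenever an efficacy boundary is crossed. They do not depend on how the base figure of 8,800 was obtained. The plan should be changed, but the trial's type I error and its ability to reach a valid decision are not in question.

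**What to change.** Add to the primary analysis: if the trial stops before the final look, the mixed-model odds ratio will be reported together with a median-unbiased estimate and a 95% interval from stagewise ordering, based on the gamma(-4) efficacy boundary; conclusions about effect size will rest on the adjusted interval. The prespecified model estimate need not be relegated to a supplement.

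Two further cases need a sentence each, because the efficacy-boundary interval does not settle them: how the interval is computed after an actual futility stop (where overall coverage would otherwise be about 93.3%), and what is reported if the DSMB continues past a crossed boundary. A repeated confidence interval is one candidate for both, since its coverage does not depend on the stopping rule, at the price of extra width. The confidence level and the sidedness of the 0.05 should be stated at the same time.

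The cost is a few sentences and standard group-sequential software, with no change to sample size, boundaries or conduct. The downside is that the reported effect and interval after an early efficacy stop become somewhat less favourable.
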